1.3 Treatments

Table 1-3 presents the study products.

Table 1-3 Investigational/Study Product Supplies

Product Description	Test Product	Reference Product
Product Name	Corsodyl Original Toothpaste	Colgate Cavity Protection Toothpaste
Pack Design	Carton of 6 over-wrapped tubes	
Dispensing Details	One carton – baseline visit	
Product Master Formulation Code (MFC)	CCI [REDACTED] (Commercial Product)	Commercial Product
Dose Application	Full ribbon of toothpaste on head of toothbrush provided	
Route of Administration	Oral	
Usage Instructions	Subjects will brush their teeth for at least a minute twice a day (morning and evening)	
Return Requirements	All used/unused samples to be returned	

Detailed instructions for the return of study product/study supplies for the accountability checks and subsequent destruction which will be provided by the sponsor during the study in time for study close out visit.

1.4 Sample Size Calculation

A sample size of approximately 100 subjects per treatment group (before presumed 6% dropout rate) is needed to provide at least 90% power to achieve statistical significance (at the 5%, two-sided level) for the primary outcome (change from baseline at 12 weeks in the number of bleeding sites in the sodium bicarbonate group). The assumed treatment efficacy estimates for this calculation comes from the sponsor clinical study (CCI [REDACTED] 2012) report where the change (SD) from baseline at 12 weeks (without pre-prophylaxis) was -14.7 (9.8) bleeding sites.

For the secondary objective (change from baseline at 12 weeks in the number of bleeding sites in the bicarbonate group compared to the negative control group), data from the sponsor clinical study (CCI [REDACTED] 2012) focusing on the non-smoking strata and using a t-test comparing their respective mean changes (SD of change) of 15.5 (10.1) vs. 11.6 (9.1) indicates power will exceed 80%. (PASS 2019 Power Analysis and Sample Size Software (2019). NCSS, LLC. Kaysville, Utah, USA, ncss.com/software/pass). The assumed (from the sponsor clinical study CCI [REDACTED] 2012) +0.7 correlation of the number of bleeding sites at baseline to week 12 helps attain that power.

2 Planned Analyses

2.1 Interim Analysis

No interim analysis is planned.

2.2 Final Analyses

The final planned primary analyses will be performed after the completion of the following sequential steps:

1. All subjects have completed the study as defined in the protocol.
2. All required database cleaning activities including any external data reconciliation have been completed and the database has been locked.
3. All criteria for unblinding the randomization codes have been met and the randomization codes have been distributed.

3 Considerations for data analyses and Data Handling Conventions

3.1 Baseline Definition

For all endpoints, the baseline value will be the Day 0 (Visit 2) pre-brushing assessment with a non-missing value.

Unless otherwise stated, if baseline data is missing no derivation will be performed and the baseline value will be set to missing.

3.2 Subgroups/Stratifications

No subgroups or stratification factors are defined in this study.

3.3 Centers Pools

Since this is a single center study, pooling of centers is not applicable.

3.4 Timepoints and Visit Windows

The timepoints and visits for this study are defined in [Table 1-1](#) “Schedule of Activities”. Any deviation from the study schedule may be reviewed on a case-by-case basis at the Blind Data Review Meeting (BDRM) to determine whether the data should be excluded from the Per Protocol (PP) population.

4 Data Analysis

Data analysis will be performed by **CCI** with oversight from Haleon. The statistical analysis software used will be SAS version 9.4 or higher.

Prior to database closure a BDRM will be conducted in which various aspects of the trial will be discussed and agreed.

One aspect that will be considered prior to or during the BDRM is the assessment of the number of subjects who have dropped or discontinued from the study due to pandemic related events (e.g. Coronavirus Disease of 2019 [COVID-19]) and the potential need of a sensitivity analysis. Any major changes to planned analyses will need an amendment to the SAP.

Except as described below, all listings will be produced for all randomized subjects.

4.1 Populations for Analysis

4.1.1 Subject Disposition

Screen failures are defined as subjects who consent to participate in the clinical study but are not subsequently randomized. An enrolled subject is a subject who has signed informed consent and is eligible to proceed beyond the screening visit.

The number of subjects screened, enrolled, and randomized will be presented in Table 14.1.1.

The number and percentage of screen failure subjects (subjects not randomized) with reasons why subjects are not randomized including percentage of subjects not randomized due to the COVID-19 pandemic will be displayed. Percentages for screen failure subjects will be based on the total number of subjects screened.

The number and percentage of randomized subjects who complete and discontinue the study, broken down by reason for discontinuation including percentage of subjects discontinued/withdrew from study due to COVID-19 pandemic, by study product and overall will also be displayed. The percentages will be based on the number of subjects randomized.

Table 14.1.1 will also present the number and percentage of subjects in each of the defined analysis populations (as defined in [Section 4.1.3](#)) by study product and overall. Percentages will be based on the number of subjects randomized.

Subject disposition including demographic data (age, sex, race and ethnicity), screening date, study product start date and time, subject status (completer, Yes/No), study completion /withdrawal date, duration (in days) in the study (defined as [(date of completion or withdrawal – start date of study product use) + 1], and the primary reason for withdrawal will be listed (Listing 16.2.1.1) by study product.

Subject disposition information will be listed for non-randomized subjects (Listing 16.2.1.2), displaying subject number, demographic information (age, sex, race and ethnicity), enrolled

(Yes/No), screening date, reason for screen failure, any further details of reason for screen failure and discontinuation status due to COVID-19 pandemic.

4.1.2 Protocol Deviations

Protocol deviations will be tracked by the study team throughout the conduct of the study. Data will be reviewed prior to unblinding and closure of the database to ensure all important deviations are captured and categorized. Subjects with important protocol deviations liable to influence the efficacy outcomes will be excluded from the PP population. Subjects may also be identified as having important protocol deviations not leading to exclusion from the PP population.

Important deviations of the protocol procedures may include, but will not necessarily be limited to the following:

- Consent procedures
- Inclusion/Exclusion criteria
- Concomitant medication/therapy
- Laboratory assessments
- Study procedures
- Randomization procedures
- Study drug dosing/study product administration/study product compliance
- Visit schedule/interval
- Other

The specific details of the important protocol deviations will be listed in Protocol Deviation Management Plan, and the assessment process will be specified in the Blind Data Review Plan. Subjects with important protocol deviations will be identified at the BDRM.

The number and percentage of subjects with at least one important protocol deviation, subjects with important protocol deviations not leading to exclusion from the PP population with reasons for deviations and subjects with important protocol deviations leading to exclusion from the PP population with reasons for deviations will be presented by study product and overall for all randomized subjects (Table 14.1.2) and listed in Listing 16.2.2.1.

All protocol deviations collected on the protocol deviation case report form page will be listed in Listing 16.2.2.2. The listing will present date of deviation, type of deviation, and deviation description.

4.1.3 Analysis Populations

Five analysis populations are defined.

Population	Definition / Criteria	Analyses Evaluated
Safety	Comprise of all randomized subjects who receive at least one dose of study product. This population will be based on the product the subject actually received.	
 Demographics Safety
Modified Intent-to-Treat (mITT)	Comprise of all randomized subjects who complete at least one dose of study product and have at least one post baseline clinical performance assessment. This population will be based on the study product to which the subject was randomized. Any subject who receives a randomization number will be considered to have been randomized.	
 Demographics Compliance Efficacy
Per-Protocol (PP)	Comprise of all randomized subjects who do not have any protocol deviations that could confound the interpretation of analyses conducted on the mITT. This population will be based on the study product to which the subject was randomized. Protocol deviations that may exclude subjects from the PP population are defined in Section 4.1.2 (Protocol Deviations) .	
 Efficacy
MGI Repeatability	Comprise of all subjects who have at least one repeat MGI clinical assessment at any visit.	
 Repeatability for MGI
TPI Repeatability	Comprise of all subjects who have at least one repeat TPI clinical assessment at any visit.	
 Repeatability for TPI

NOTES:

Please refer to [Appendix 1: List of Data Displays](#), which details the population to be used for each display being generated.

The numbers of subjects included in each of the analysis populations will be summarized for all screened subjects (Table 14.1.1). Subjects excluded from any of the analysis populations will be listed in Listing 16.2.3.1.

The primary population for assessment of efficacy will be the mITT Population. A PP analysis will be performed on the primary endpoint only if more than 10% of mITT subjects are excluded from the PP Population. A decision on whether a PP analysis will be performed will be made prior to study unblinding (release of the randomization codes).

4.2 Subject Demographics and Other Baseline Characteristics

4.2.1 Demographic Characteristics

Descriptive statistics (number of subjects [n], mean, standard deviation [SD], median, minimum, and maximum for continuous variables and frequency count [n] and percentage [%] of subjects for categorical variables) will be presented for demographic variables by study

product and overall. These variables include age, gender, race, and ethnicity and will be presented for the Safety population (Table 14.1.3.1) and the mITT population (Table 14.1.3.2). Demographic information will be listed (Listing 16.2.4.1) for all randomized subjects.

4.2.2 General Medical History

Medical and surgical history (in the last year) including allergies or drug sensitivity will be listed in Listing 16.2.4.2, with start date and end date or ongoing at the start of study product.

4.3 Treatments (Study Product, Rescue Medication, other Concomitant Therapies, Compliance)

Randomization details will be listed, including the randomization number, the planned study product, the actual study product the subject was randomized to and the randomization date (Listing 16.1.7.1).

The study product kit allocations will be listed (Listing 16.1.7.2), including kit number and study product information.

4.3.1 Study Product Compliance and Exposure

Compliance data will be summarized for the mITT population and will be assessed by number of brushings.

Number of brushings, brushing compliance (%), number of missed brushings and number of additional brushings will be summarized using descriptive statistics by cumulative visit and by study product. The number and percentage of subjects <80%, between 80% - 120% and >120% compliant in each study product will also be presented by cumulative visit and by study product (Table 14.2.1).

Number of brushings is defined as: [(date of Visit x – date of Visit 2) multiplied by 2 – number of missed brushings + number of additional brushings], where $x = 3, 4$ and 5 , respectively.

Brushing compliance (%) is defined as: [100 x (Actual number of brushings / Expected number of brushings)], where expected number of brushings is defined as: [(date of Visit x – date of Visit 2) multiplied by 2].

Study product compliance (number of brushings, brushing compliance [%], number of missed brushings and number of additional brushings) will be listed in Listing 16.2.5.1 for all randomized subjects by study product.

Supervised study product application (subject number, visit, date and time of the supervised procedure) will be listed (Listing 16.2.5.2) for all randomized subjects.

4.3.2 Prior and Concomitant Medication

Prior medications/treatments, including prescription and non-prescription drugs, dietary supplements and herbal remedies, taken in the last 30 days and prior to signing the informed consent form, will be documented in the case report form (CRF). The prior and concomitant medications will be coded using a validated medication dictionary, World Health Organization Drug Dictionary (WHODD).

Prior medications and prior non-drug treatments will be listed by subject, with drug name, WHODD Drug Synonym, reason, route, dose, frequency, start date and end date both relative to study product start date (Listing 16.2.4.3) for all randomized subjects. Prior medications are defined as those which stopped before the first use of the study product.

Concomitant medications and concomitant non-drug treatments/significant non-drug therapies taken during treatment will be listed similarly (Listing 16.2.4.4) for all randomized subjects with either ongoing or end date displayed. Concomitant medications are defined as medications that started or stopped on or after the first use of the study product, or are ongoing.

Unknown dates will not be imputed. However, if the start or stop date is unknown, then it will be assumed to be concomitant medication unless the partial start date or stop date indicates differently.

4.4 Analysis of Efficacy

The primary population for assessment of efficacy will be the mITT population. No repeat assessment data is to be used in any efficacy analyses.

Statistical analyses of the endpoints will be performed using the change from baseline, in order to easily present direct estimates for the within-treatment mean changes from baseline (e.g. the primary endpoint).

Descriptive summary statistics will be presented for the actual and change from baseline values at each time point.

All p-values presented will be two-sided and assessed at the 5% significance level. A sequential testing strategy will be used to adjust for multiplicity for the comparison between test and reference products in the number of bleeding sites at Week 12. This will only be assessed for confirmatory evidence if the primary endpoint (change from baseline within the test product at Week 12) achieves a statistically significant reduction. There will be no further adjustments for multiplicity for any other secondary endpoints.

4.4.1 Primary Efficacy Endpoint

4.4.1.1 Primary Efficacy Endpoint Definition

The primary endpoint for the study is the change from baseline number of bleeding sites at 12 weeks in the Test Product group in the mITT population.

The BI will be assessed on the facial and lingual gingival surfaces of each scorable tooth (7-7 in each arch). Three scores (according to the scale in **Table 4-1** below) should be recorded buccally/labially (distal, body and mesial sites) and three scores lingually/palatally (distal, body and mesial sites). At each visit, each subject therefore has up to 168 evaluable tooth sites (i.e. 6 measurements on up to 28 scorable teeth).

Table 4-1 Bleeding Index Scoring System

Score Description	
0	No bleeding after 30 seconds
1	Bleeding observed within 30 seconds of probing
2	Bleeding observed immediately on probing
9	Missing tooth or not qualified tooth

The number of bleeding sites for each subject at each visit is calculated as the number of evaluable tooth sites with a BI score of either 1 or 2, to give a count between 0 and 168.

Descriptive statistics (n, mean SD, standard error [SE], median, minimum, and maximum) will be presented for the number of bleeding sites at each time point (absolute value, change from baseline and percent change from baseline) in Table 14.2.2.1.1 for all subjects in the mITT population by study product. Raw means (\pm SE) of the number of bleeding sites at each time point will be plotted by study product in Figure 14.2.2.1.5 for all subjects in the mITT population.

Additionally, the number and percentage of subjects whose number of bleeding sites has reduced (improved), remained the same and increased (worsened), respectively compared to baseline, will be presented by study product at each time point in Table 14.2.2.1.3 for the mITT population.

Individual data for the number of bleeding sites will be listed for each subject by study product group and visit in Listing 16.2.6.1 for all randomized subjects.

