4.4.1.2 Statistical Hypothesis, Model, and Method of Analysis

The following null and alternative hypotheses will be evaluated:

- H_0 : There is no difference in the number of bleeding sites from baseline to Week 12 in the Test Product group.
- H_1 : There is a treatment effect on the number of bleeding sites at Week 12, compared to baseline, in the Test Product group.

A Mixed Model for Repeated Measures (MMRM) will be used, with change from baseline in number of bleeding sites as the dependent variable, the categorical time point (Week 3, Week 6, or Week 12), treatment group (Test Product or Reference Product) and time point \times treatment group interaction as fixed effects, and baseline number of bleeding sites as a covariate. Subject will be included as a repeated measure with an unstructured covariance matrix. The Kenward

Roger degrees of freedom approach will be applied. If unstructured covariance matrix does not converge, the following covariance structures will be applied in order until convergence is achieved: 1) Toeplitz, 2) compound symmetry (CS).

Using the above model, the LS mean change from baseline number of bleeding sites will be presented for the Test Product at Week 12, along with 95% CI and p-value, testing for a non-zero change from baseline (Table 14.2.2.1).

The assumption of normality and homogeneity of variance in the MMRM will be investigated. In case of violation of these assumptions, a Wilcoxon Signed Rank Test (within product comparisons with baseline) will be performed to support the MMRM results.

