4.4.1.3 Supportive Analyses

A PP analysis will be performed on the number of bleeding sites if there is more than a 10% difference in the number of subjects between the PP and mITT populations. A decision on whether a PP analysis will be performed will be made prior to study unblinding (release of randomization codes).

A summary of the mean number of bleeding sites at each time point will be presented for the PP population in Table 14.2.2.1.2. A summary of the number and percentage of subjects at each time point whose number of bleeding sites has improved/remained the same/worsened compared to baseline will be presented for the PP population in Table 14.2.2.1.4. Statistical analysis of the mean number of bleeding sites will be presented for the PP population in Table 14.2.2.2.2. In addition, the mean number of bleeding sites at each time point will be plotted by study product for all subjects in the PP population (Figure 14.2.2.1.6).

In order to explore the sensitivity of results to the effect of missing data, the MMRM model described in [Section 4.4.1.2](#) will be repeated using the LOCF approach for the mITT population (Table 14.2.2.2.3) and the PP population (Table 14.2.2.2.4).

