4.4.2.2 Change from Baseline in Bleeding Index (BI)

The BI will be assessed at each evaluable tooth site for each subject at each visit as described in [Section 4.4.1.1](#), according to the scoring system in [Table 4-1](#). The BI score for each subject at each visit is calculated as the sum of index values over all evaluable tooth sites, divided by the number of evaluable tooth sites. Evaluable tooth sites are those scored as 0, 1 or 2, so the BI score has a range of 0 to 2.

Descriptive statistics (n, mean, SD, SE, median, minimum, and maximum) will be presented for the BI score at each time point (absolute value, change from baseline and percent change

from baseline) in Table 14.2.3.1.1. Raw means (\pm SE) of the BI score at each time point will be plotted by study product in Figure 14.2.3.1.3 for all subjects in the mITT population.

Additionally, the number and percentage of subjects whose BI score has reduced (improved), remained the same and increased (worsened), respectively compared to baseline, will be presented by study product at each time point in Table 14.2.3.1.2 for the mITT population.

Individual data for the BI assessment at each evaluable tooth site will be listed for each subject in Listing 16.2.6.2.1, and individual data for the derived BI score will be listed for each subject in Listing 16.2.6.2.2, by study product group and visit for all randomized subjects.

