4.4.2.2.1 Statistical Hypothesis, Model and Method of Analysis

For comparisons to baseline within each treatment group, the following null and alternative hypotheses will be evaluated for post-baseline time points at Week 3, Week 6 and Week 12, respectively:

- H_0 : There is no difference in the BI score from baseline.
- H_1 : There is a treatment effect on the BI score compared to baseline.

For comparisons to negative control, the following null and alternative hypotheses will be evaluated for post-baseline time points at Week 3, Week 6, and Week 12, respectively:

- H_0 : There is no difference in change from baseline in the BI score in the Test Product group compared to the Reference Product group.
- H_1 : There is a difference in change from baseline in the BI score in the Test Product group compared to the Reference Product group.

A MMRM will be used as described in [Section 4.4.1.2](#), with change from baseline in BI score as the dependent variable and baseline BI score as a covariate instead of baseline number of bleeding sites.

Using the above model, the LS mean change from baseline BI score will be presented for each study product at each post-baseline time point with corresponding 95% CIs and p-values to test for a non-zero change from baseline.

The difference in LS mean change from baseline BI score (Test Product – Reference Product) will also be presented at each post-baseline time point with corresponding 95% CIs and p-values to test for a non-zero difference (Table 14.2.3.2.1).

The assumption of normality and homogeneity of variance in the MMRM will be investigated. In case of violation of these assumptions, a Wilcoxon Rank Sum test (between products comparisons) and Wilcoxon Signed Rank Test (within product comparisons with baseline) will be performed to support the MMRM results.

The MMRM model will be repeated using the LOCF approach for the mITT population (Table 14.2.3.2.2).

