4.4.3 Handling of Missing Values/Censoring/Discontinuations

For the primary analyses, missing data will not be replaced or imputed. Subjects who withdraw from the study prematurely will be included in the statistical analyses up to the point of discontinuation. Subjects who withdraw will not be replaced. In the event that a subject has no individual BI, MGI or TPI assessments available at a given visit, the number of bleeding sites, BI score, MGI score or TPI score will also be considered as missing for that visit.

Experience in previous, similar studies suggest missing data will not be prevalent. The SAS Proc Mixed implementation of the repeated measures analysis of covariance (ANCOVA) that will be used in almost all analyses, implicitly imputes any missing data based on the non-missing observations. The basic theory on which Proc Mixed is based holds even with missing data as long as the missing data are missing at random.

An additional analysis will explore the sensitivity of results to the effect of missing data on the primary and secondary efficacy endpoints. The sensitivity analysis will use the same MMRM model, but with LOCF for missing data. Only post-baseline results may be carried forward.

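### Does the primary bleeding-site count need a rule or an extra analysis for sites that stop being scorable after baseline?

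*SAP*

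**What the plan says.** SAP 4.4.1.1 and protocol 9.2.2 define the number of bleeding sites identically: for each subject and visit it is "calculated as the number of evaluable tooth sites with a BI score of either 1 or 2". The SAP gives the range as 0 to 168, and Table 4-1 adds code 9, "Missing tooth or not qualified tooth".

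The model in SAP 4.4.1.2 analyses the change in this count, with "baseline number of bleeding sites as a covariate".

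SAP 4.4.3 sets the count to missing only for a visit with nothing scored: "In the event that a subject has no individual BI, MGI or TPI assessments available at a given visit". Partial loss of sites has no rule. The missing-data analysis in SAP 4.4.1.3, introduced by "In order to explore the sensitivity of results to the effect of missing data", is the same model with LOCF.

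Mean BI (SAP 4.4.2.2) is the "sum of index values over all evaluable tooth sites, divided by the number of evaluable tooth sites". SAP 4.4.2.2.1 fits the same model to it, "with change from baseline in BI score as the dependent variable and baseline BI score as a covariate".

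Several protocol passages point to a stable set of sites without fixing it. Section 4.1 ties evaluable teeth to the entry dentition criteria, section 5.2 judges calculus by whether it interferes with the baseline assessments, and section 9.2.2 has BI scored on evaluable teeth from Baseline on.

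**The concern.** In a raw count, a 9 and a 0 contribute the same amount: nothing. A subject can appear to improve because a bleeding tooth can no longer be scored. The reverse also holds, since a site coded 9 at baseline and scored later can only add to the count.

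Suppose 30 of 168 sites bleed at baseline, two teeth holding 8 of them are coded 9 at week 12, and nothing else changes. The count goes from 30 to 22, a change of -8, and the subject is tabulated as improved. On the 156 sites scored at both visits the change is 0.

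LOCF does not touch this, because a partly scored visit is not missing. The per-protocol and Wilcoxon analyses reuse the same count. At stake would be an inflated within-arm reduction and, if loss differed by arm, a biased week 12 comparison with the reference product, which is the second step of the testing sequence. Loss is conceivable: there is no cleaning at entry, and surfaces with interfering calculus are not evaluable.

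**Working it through.** **The plan's own figures (SAP 1.4)**

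- Evaluable subjects: 100 × (1 - 0.06) = 94 per arm.
- Primary: change 14.7, SD 9.8, n = 94. SE = 9.8/√94 = 1.01. One-sample t power exceeds 99.9%, and 7 subjects would already give 90%.
- Between arms: 15.5 - 11.6 = 3.9. Pooled SD = √((10.1² + 9.1²)/2) = 9.61. SE = √((10.1² + 9.1²)/94) = 1.40. Two-sample t power is 79.0% with 94 per arm and 81.5% with 100.
- Adjusting for baseline with correlation 0.7 and equal variances at both visits (assumed): residual SD = √(9.61²/(2 × 0.3) × (1 - 0.49)) = 8.86, and power with 94 per arm is 85.1%. The stated power above 80% is reproduced on this basis.

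**Size of the artefact**

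What drops out is the bleeding that would have been seen at week 12, so:

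shift in the arm mean = share of subjects with a tooth newly coded 9 × 6 sites × week 12 bleeding rate

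Sites per subject run from 120 (40 surfaces × 3, protocol 5.2) to 168. Baseline bleeding is taken as 20%, the middle of the 10-30% entry range (assumed).

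| | 120 sites | 168 sites |
|---|---|---|
| Baseline bleeding sites | 24.0 | 33.6 |
| Week 12 rate, test arm, change 14.7 | 9.3/120 = 7.75% | 18.9/168 = 11.25% |
| One tooth (× 6) | 0.465 | 0.675 |
| Non-smoker test arm, change 15.5, one tooth | 6 × 8.5/120 = 0.425 | 6 × 18.1/168 = 0.646 |
| Non-smoker reference arm, change 11.6, one tooth | 6 × 12.4/120 = 0.62 | 6 × 22.0/168 = 0.786 |

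The share of subjects affected is not in the documents; 2% to 25% is assumed.

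- Test arm: 0.02 × 0.465 = 0.01 to 0.25 × 0.675 = 0.17 sites. The upper figure is 0.169/14.7 = 1.2% of the effect and 0.169/1.01 = 0.17 SE.
- Upper figure at 15% baseline bleeding: 0.25 × 6 × 10.5/168 = 0.09. At 25%: 0.25 × 6 × 27.3/168 = 0.24, or 1.7% of 14.7.
- If the affected teeth bleed at twice the subject's average rate, the 20% upper figure becomes 2 × 0.169 = 0.34, or 2.3% of 14.7.
- Between arms, a 10-point imbalance gives 0.10 × 0.425 = 0.04 to 0.10 × 0.786 = 0.08 sites. That is at most 2.0% of 3.9 and 0.08/1.40 = 0.06 SE.
- Equal loss nearly cancels. With 25% affected in both arms it leaves 0.25 × (0.62 - 0.425) = 0.05 sites, in the reference product's favour.

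**What it would take to matter**

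The smallest significant primary change is about 2.01 sites, so 14.7 - 2.01 = 12.7 sites would have to be artefact. At 30% bleeding that is 12.7/1.8, about 7 teeth per subject; if every affected site bled, it is 12.7/6, about 2 teeth per subject.

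**Whether rescaling to the baseline number of sites would help**

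In the two-tooth example, 22 × 168/156 = 23.7, a change of -6.3 where the true change is 0. About 6.3/8 = 79% of the artefact remains. Rescaling removes the shift only when the affected sites bleed at the subject's average rate.

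**The case for a change.** The best case for a change runs as follows. The definition has a real hole, in the primary variable, and no planned count-based analysis would reveal it. Mean BI is a graded 0-2 score, is not named as a check, and does not return a corrected number of sites. It is also only a partial check: in the two-tooth example the bleeding proportion still falls from 30/168 = 17.9% to 22/156 = 14.1%. The between-arm step is the more exposed one. With 0.1 to 1 tooth per subject newly coded 9 and 10-30% of its sites bleeding, the shift is 0.06 to 1.8 sites. If all of it fell in one arm, the top of that range is 1.8/3.9 = 46% of the planned difference. With no true difference, imbalances of 0.3, 0.6 and 1.8 sites would raise the 5% error to 5.6%, 7.5% and 28%. A check would be cheap.

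The reading of the text stands, and so does the point that differential loss is the route by which harm could come. The size does not carry over. The top figure needs every subject in one arm to have a whole tooth newly coded 9 and nobody in the other, and it applies the upper end of the entry bleeding range at week 12. Protocol 5.3 excludes pockets over 3 mm, numerous poor restorations and caries that could compromise outcomes. Section 9.3.2 excludes subjects needing extensive dental therapy, and section 5.5.3 defers non-emergency treatment. The examiner is single and blinded, and nothing in the documents suggests that loss would differ by product.

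The plan is not blind to the issue either. Site-level BI scores go into Listing 16.2.6.2.1 by subject and visit, hard tissue is re-examined at Visit 5, protocol 9 requires missed assessments to be documented as deviations, and protocol 12.3.5 and SAP 4.1.2 provide for review before unblinding.

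**Conclusion.** No change is needed. The text leaves a gap, but it matters only when a site changes status after baseline, and the documents point to that being uncommon over 12 weeks. On the assumed 2% to 25% of subjects with one affected tooth and 20% baseline bleeding, the primary mean moves by 0.01 to 0.17 sites. The alternative assumptions tried (25% baseline bleeding, or affected teeth bleeding at twice the average rate) raise the upper figure to 0.24 or 0.34 sites. All of these are small beside a planned change of 14.7 and a standard error of 1.01. The between-arm difference moves by 0.04 to 0.08 sites under a 10-point imbalance.

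The loss rate is an assumption, so the true size is unknown but probably negligible. The primary conclusion is not at risk under any loss rate one would expect.

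An added analysis would leave the primary definition as it is and serve mainly to show that a small effect is small. The simplest candidate, proportional rescaling, fails when the affected sites bled more than average. Mean BI gives a partial check. If the listings showed many status changes, the change on sites scored 0-2 at both visits could be computed from data already collected.
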